7.9. Bladder and Kidney Ultrasound

Bladder and Kidney ultrasound results will not be summarized and will be provided in the listing.

8. COVID-19 CONSIDERATIONS

This study was conducted during the COVID-19 global pandemic. During the time period of the pandemic, it is anticipated that changes in study visit schedules, missed visits, or patient discontinuations may lead to missing information (e.g., for protocol-specified procedures). In accordance with the FDA guidance of conduct of clinical trials of medical products during COVID-19 public health emergency, it is important to capture specific information in the case report form that explains the basis of the missing data, including the relationship to COVID-19 for missing protocol-specified information (e.g., from missed study visits or study discontinuations due to COVID-19).

The proportion of subjects with COVID-19 impact on visits will be summarized by treatment group overall and by visit. The reasons (e.g. subject acquired COVID-19, Subject unable to travel due to COVID-19, investigative site closure due to COVID-19, etc) will also be summarized. A listing of subjects who had a COVID-19 information collected will be generated which will document the date of contact, update to AE or concomitant medication since the last visit, and whether the bladder diaries were completed.

9. CHANGE FROM ANALYSIS PLANNED IN PROTOCOL

[figure not shown]
Protocol section 9.3 defined analyses population. In the SAP [Section 3.1](#), safety (modified) population was removed.

Protocol section 3.2.1 defined exploratory efficacy endpoints. In the SAP [Section 1.1.1](#) and [Section 4.3.2](#) , ‘Nighttime voids’ was added as an exploratory efficacy endpoint.

In the SAP [Section 7.2](#) the definition of treatment-emergent adverse event was updated to include the additional OAB medication as the end of the treatment-emergent period in addition to the initiation of the investigational agent and/or surgical intervention.

In Protocol section 9.5.1 PGI-C change from baseline was analyzed using MMRM method. In the SAP section 4.3.3 and 6.2 the analysis method for PGI-C was changed to use the responder analysis with CMH method.

SAP added additional endpoint of proportion of subjects achieving $\geq 50\%$, $\geq 75\%$ and 100% reduction in average daily UI episodes.

Since no analysis plan is definitive especially for this exploratory study, we may perform additional data driven sensitivity analysis.

11. APPENDIX

11.1. Table of Contents for Data Display Specifications

11.1.1. Output Tables

Table 8: List of Output Tables

Title		Population	Programming Note	Deliverable
Study Population				
14.1.1.1	Subject Enrollment	Scanned		EOS
14.1.1.2	Subject Disposition	Randomized		TL, EOS
14.1.1.3	Subject Randomization by Investigator	Randomized		EOS
14.1.2.1	Major Protocol Deviations	Randomized		EOS
14.1.2.2	Reasons for Exclusion from Analysis	Randomized		EOS
14.1.3.1	Demographics and Baseline Characteristics	ITT-E		TL, EOS
14.1.4	Medical History	ITT-E		EOS
14.1.5.1	Prior Medication	ITT-E	ATC Level 2 and 4	EOS
14.1.5.2	Concomitant Medication	ITT-E	ATC Level 2 and 4	EOS
14.1.5.3	Additional OAB Treatment Received Prior to Week 24 (Medication)	ITT-E	ATC Levels 2, 4 and PT	TL, EOS
14.1.5.4	Additional OAB Treatment Received at or After Week 24 (Medication)	ITT-E	ATC Levels 2, 4 and PT	TL, EOS
14.1.5.5	Additional OAB Treatment Received Prior to Week 24 (Procedure)	ITT-E	ATC Levels 2, 4 and PT	EOS

Title		Population	Programming Note	Deliverable
14.1.5.6	Additional OAB Treatment Received at or After Week 24 (Procedure)	ITT-E	ATC Levels 2, 4 and PT	EOS
14.1.6	COVID-19 Impact	ITT-E		EOS
Efficacy Endpoints				EOS
14.2.1.1	Change from Baseline in Average Daily Number of Urge Urinary Incontinence Episodes (MMRM)	ITT-E	Week 12 first, then other visits sequentially	TL, EOS
14.2.1.2	Summary of Average Daily Number of Urge Urinary Incontinence Episodes	ITT-E	By-visit Descriptive Summary	TL, EOS
14.2.1.3	Summary of Average Daily Number of Urge Urinary Incontinence Episodes by Baseline UUI Episodes per Day	ITT-E	Subgroup columns within each treatment arm	EOS
14.2.1.4	Summary of Average Daily Number of Urge Urinary Incontinence Episodes by Presence or absence of DO	ITT-E	Subgroup columns within each treatment arm	EOS
14.2.1.5	Summary of Average Daily Number of Urge Urinary Incontinence Episodes by Previous Use of onabotulinumtoxinA	ITT-E	Subgroup columns within each treatment arm	EOS
14.2.1.6	Change from Baseline in Average Daily Number of Urge Urinary Incontinence Episodes at Week 12	ITT-E		EOS
14.2.1.7	Change from Baseline in Average Daily Number of Urge Urinary Incontinence Episodes (MMRM) - Sensitivity Analysis	ITT-ES	Week 12 first, then other visits sequentially	EOS
14.2.2.1	Change from Baseline in Average Daily Number of Micturitions (MMRM)	ITT-E	Week 12 first, then other visits sequentially	TL, EOS
14.2.2.2	Summary of Average Daily Number of Micturitions	ITT-E	By-visit Descriptive Summary	TL, EOS
14.2.2.3	Summary of Average Daily Number of Micturitions by Baseline UUI Episodes per Day	ITT-E	Subgroup columns within each treatment arm	EOS
14.2.2.4	Summary of Average Daily Number of Micturitions by Presence or absence of DO	ITT-E	Subgroup columns within each treatment arm	EOS

Title		Population	Programming Note	Deliverable
14.2.2.5	Summary of Average Daily Number of Micturitions by Previous Use of onabotulinumtoxinA	ITT-E	Subgroup columns within each treatment arm	EOS
14.2.2.6	Change from Baseline in Average Daily Number of Micturitions at Week 12	ITT-E		EOS
14.2.2.7	Change from Baseline in Average Daily Number of Micturitions (MMRM) - Sensitivity Analysis	ITT-ES	Week 12 first, then other visits sequentially	EOS
14.2.3.1	Change from Baseline in Average Daily Number of Urinary Incontinence Episodes (MMRM)	ITT-E	Week 12 first, then other visits sequentially	TL, EOS
14.2.3.2	Summary of Average Daily Number of Urinary Incontinence Episodes	ITT-E	By-visit Descriptive Summary	TL, EOS
14.2.3.3	Summary of Average Daily Number of Urinary Incontinence Episodes by Baseline UUI Episodes per Day	ITT-E	Subgroup columns within each treatment arm	EOS
14.2.3.4	Summary of Average Daily Number of Urinary Incontinence Episodes by Presence or absence of DO	ITT-E	Subgroup columns within each treatment arm	EOS
14.2.3.5	Summary of Average Daily Number of Urinary Incontinence Episodes by Previous Use of onabotulinumtoxinA	ITT-E	Subgroup columns within each treatment arm	EOS
14.2.4.1	Change from Baseline in Average Daily Number of Urgency Episodes (MMRM)	ITT-E	Week 12 first, then other visits sequentially	TL, EOS
14.2.4.2	Summary of Average Daily Number of Urgency Episodes	ITT-E	By-visit Descriptive Summary	TL, EOS
14.2.4.3	Summary of Average Daily Number of Urgency Episodes by Baseline UUI Episodes per Day	ITT-E	Subgroup columns within each treatment arm	EOS
14.2.4.4	Summary of Average Daily Number of Urgency Episodes by Presence or absence of DO	ITT-E	Subgroup columns within each treatment arm	EOS
14.2.4.5	Summary of Average Daily Number of Urgency Episodes by Previous Use of onabotulinumtoxinA	ITT-E	Subgroup columns within each treatment arm	EOS
14.2.5.1	Change from Baseline in Average Volume Voided per Micturition (MMRM)	ITT-E	Week 12 first, then other visits sequentially	TL, EOS

Title		Population	Programming Note	Deliverable
14.2.5.2	Summary of Average Volume Voided per Micturition	ITT-E	By-visit Descriptive Summary	TL, EOS
14.2.6.1	Proportion of Subjects Achieving $\geq 50\%$ Reduction in Number of Average Daily Urge Urinary Incontinence Episodes from Baseline	ITT-E	Week 12 first, then other visits sequentially	EOS
14.2.6.2	Proportion of Subjects Achieving $\geq 75\%$ Reduction in Urge Urinary Incontinence Episodes from Baseline	ITT-E	Week 12 first, then other visits sequentially	EOS
14.2.6.3	Proportion of Subjects achieving 100% Reduction in Urge Urinary Incontinence Episodes from Baseline	ITT-E	Week 12 first, then other visits sequentially	TL, EOS
14.2.7.1	Change from Baseline I-QOL Domains (MMRM)	ITT-E	Week 12 first, then Week 6	TL, EOS
14.2.7.2	Summary of I-QOL Scores	ITT-E	By-visit Descriptive Summary	TL, EOS
14.2.7.3	Proportion of Subjects Achieving the Minimally Important Difference in I-QOL Total Summary Score	ITT-E	Week 12 first, then Week 6	EOS
14.2.8.1	Change from Baseline in OAB-q Scores (MMRM)	ITT-E	Week 12 first, then Week 6	TL, EOS
14.2.8.2	Summary of OAB-q Scores	ITT-E	By-visit Descriptive Summary	TL, EOS
14.2.9.1	Change from Baseline on Patient Global Impression Change Score at Week 12	ITT-E	Week 12 only	TL, EOS
14.2.9.2	Summary of Patient Global Impression	ITT-E	By-visit Descriptive summary and change from baseline of numeric score	EOS
14.2.10	Summary of Urodynamic Parameters	ITT-E	Baseline and Week 12 only	EOS
14.2.11	Summary of hSlo cDNA Concentrations	ITT-E		TL, EOS
14.2.12.1	Change from Baseline in Average Daily Number of Nighttime Voids (MMRM)	ITT-E	Week 12 first, then other visits sequentially	EOS

Title		Population	Programming Note	Deliverable
14.2.12.2	Summary of Average Daily Number of Nighttime Voids	ITT-E	By-visit Descriptive Summary	EOS
14.2.13.1	Proportion of Subjects Achieving $\geq 50\%$ Reduction in Number of Average Daily Urinary Incontinence Episodes from Baseline	ITT-E	Week 12 first, then other visits sequentially	EOS
14.2.13.2	Proportion of Subjects Achieving $\geq 75\%$ Reduction in Number of Average Daily Urinary Incontinence Episodes from Baseline	ITT-E	Week 12 first, then other visits sequentially	EOS
14.2.13.3	Proportion of Subjects Achieving 100% Reduction in Number of Average Daily Urinary Incontinence Episodes from Baseline	ITT-E	Week 12 first, then other visits sequentially	EOS
Safety Endpoints				
Adverse Events				
14.3.1.1	Overall Treatment-Emergent Adverse Events	Safety		TL, EOS
14.3.1.2.1	Treatment-Emergent Adverse Events by System Organ Class and Preferred Term	Safety	Sort by SOC and PT in descending frequency of URO-902 arms combined.	TL, EOS
14.3.1.2.2	Treatment-Emergent Adverse Events Occurring between Weeks 1 and 24 by System Organ Class and Preferred Term	Safety	Sort by SOC and PT in descending frequency of URO-902 arms combined.	EOS
14.3.1.2.3	Treatment-Emergent Adverse Events Occurring between Weeks 24 and 48 by System Organ Class and Preferred Term	Safety	Sort by SOC and PT in descending frequency of URO-902 arms combined.	EOS
14.3.1.3.1	Treatment-Emergent Adverse Events by Preferred Term	Safety	Sort by PT in descending frequency of URO-902 arms combined. Same for all subsequent tables	TL, EOS
14.3.1.3.2	Treatment-Related Treatment-Emergent Adverse Events by Preferred Term	Safety		EOS

Title		Population	Programming Note	Deliverable
14.3.1.4	Treatment-Emergent Adverse Events by Preferred Term and Maximum Intensity	Safety		EOS
14.3.1.5	Treatment-Emergent Adverse Events with Grade ≥ 3 by Preferred Term	Safety		EOS
14.3.1.6	Treatment-Related Treatment-Emergent Adverse Events with Grade ≥ 3 by Preferred Term	Safety		EOS
14.3.1.7	Serious Treatment-Emergent Adverse Events by Preferred Term	Safety		TL, EOS
14.3.1.8	Treatment-Related Serious Treatment-Emergent Adverse Events by Preferred Term	Safety		EOS
14.3.1.9	Fatal Treatment-Emergent Adverse Events by Preferred Term	Safety		EOS
14.3.1.10	Treatment-Emergent Adverse Events Leading to Study Discontinuation by Preferred Term	Safety		TL, EOS
14.3.1.11	Treatment-Emergent Adverse Events of Special Interest by Preferred Term	Safety		EOS
14.3.1.12	Treatment-Related Treatment-Emergent Adverse Events of Special Interest by Preferred Term	Safety		EOS
14.3.1.13	Non-Fatal Serious Treatment-Emergent Adverse Events by Preferred Term	Safety		EOS
14.3.1.14	Adverse Events Occurred After Study Dose Through Week 48 and After Initiation of Another OAB Medication, Investigational Agent, or Surgical Intervention	Safety	Same Layout as the Overall AE Summary Table 14.3.1.1	EOS
14.3.2.6	List of Deaths	Safety		EOS
14.3.2.7	Listing of Serious Adverse Events	Safety		EOS
14.3.2.8	Listing of Treatment-Emergent Adverse Events Leading to Study Discontinuation	Safety		EOS

Title		Population	Programming Note	Deliverable
14.3.2.9	Listing of Treatment-Emergent Adverse Events of Special Interest	Safety		EOS
Laboratory data				
14.3.3.1	Hematology Laboratory Parameters	Safety	Include observed and CFB	EOS
14.3.3.2	Abnormal Classification of Hematology Laboratory Parameters	Safety		EOS
14.3.3.3	Shift Table of L/N/H Classification for Hematology Laboratory Parameters from Baseline	Safety	Include max/min post-dose, by visit, last-post dose	EOS
14.3.3.4	Clinical Chemistry Laboratory Parameters	Safety	Include observed and CFB	EOS
14.3.3.5	Abnormal Classification of Clinical Chemistry Laboratory Parameters	Safety		EOS
14.3.3.6	Shift Table of L/N/H Classification for Clinical Chemistry Laboratory Parameters from Baseline	Safety	Include max/min post-dose, by visit, last-post dose	EOS
Other Safety				
14.3.4	Vital Sign Parameters	Safety	Include all observed and CFB	EOS
14.3.5	Electrocardiograms Parameters	Safety	Include all observed and CFB	EOS
14.3.6	Physical Examination Shift from Baseline	Safety		EOS
14.3.7	Post-void Residual Urine Volume	Safety	Include all observed and CFB	TL, EOS
14.3.8	Clean Intermittent Catheterization	Safety		EOS

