3.1.3. Safety Population

The safety population consists of all subjects from Cohorts 1 and 2 who were randomized and received study drug and will be used to analyze all safety endpoints based on actual treatment received.

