3.1.4. Intent-to-treat Exposed (ITT-E)

The ITT-E population consists of all subjects who are randomized and treated from Cohorts 1 and 2. ITT-E will be used for demographics, baseline characteristics, and efficacy analyses. Subjects will be included in the treatment group to which they are randomized.

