3.2.1. Protocol Deviations

The final list of major protocol deviations will be finalized and documented prior to database lock except for the deviation category of wrong treatment which will be confirmed upon study unblinding. Only major protocol deviations will be summarized and listed in the Clinical Study Report (CSR). Major deviations will be those which are considered to potentially impact upon the interpretation of the primary efficacy endpoint in the study or may potentially impact the interpretation of safety. Major protocol deviation categories may include, but are not limited to the following:

- Randomized subjects who do not meet the inclusion criteria
- Randomized subjects who meet any of the exclusion criteria
- Subjects who received the wrong treatment

- Concomitant use of prohibited medications not approved by the medical monitor
- Randomized subjects who met withdrawal criteria during the study but were not withdrawn

Due to the limited sample size of the study, no sensitivity analysis will be performed on a per-protocol population.

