4.2.2. Reporting Conventions

General rules

In general, all collected safety data, any derived efficacy parameters from the bladder diary, questionnaire data, and urodynamic data will be presented in subject data listings. Listings will be ordered by treatment, subject number, and assessment week or event date. The treatment group presented in listings will be based on the planned assignment for efficacy endpoints and actual assignment for safety endpoints.

Summary tables will be provided for all randomized subjects. All demographic and baseline data will be presented by treatment arm and overall, unless otherwise specified. Bladder diary, questionnaire, urodynamic data, and safety data will be presented by treatment arm only. In general, continuous variables will be summarized to include the population sample size (N), number of subjects with available data (n), arithmetic mean, standard deviation (SD), median, minimum, Q1, Q3 and maximum values. Categorical variables will be summarized by the population size (N), number of subjects with available data (n), number of subjects in each category, and the percentage of subjects in each category. Unless otherwise noted, the denominator to determine the percentage of subjects in each category will be based on the number of subjects with available data (n) in the analysis set of interest. Selective ordinal data may be summarized using both descriptive statistics as well as counts and percentages of subjects in each category, as appropriate.

The data analyses will be conducted using the SAS® System (SAS Institute Inc., Cary, NC) version 9.3 or above. The eClinical Solutions' standard operating procedures will be followed for the validation of all SAS programs and outputs.

Formats

Numeric data will be reported at the precision collected on the electronic case report form (eCRF). The reported precision from non eCRF sources may be adjusted to a clinically interpretable number or decimal places.

Unscheduled Visits

Unscheduled visits will be assigned to an analysis visit using the all-inclusive windows defined in [Section 4.2.4](#). If multiple assessments are done in the same visit, the selection rule in [Section 4.2.4](#) will apply. All assessments at unscheduled visits will be included for deriving last post-baseline or maximum value post-baseline and in the data listings.

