5.4. Prior and Concomitant Medication

Prior and concomitant medications will be coded using the World Health Organization (WHO) Drug B3-Sept Format, 2019 version. These medications will be further classified as follows.

- Prior medication is defined as those medications that started prior to the study treatment.
- Concomitant medication is defined as those taken on or after the study treatment. If medications started prior to the study treatment and were ongoing after the study treatment, those medication will be considered as concomitant medication as well.

The number and percentage of subjects taking prior and concomitant medications will be summarized overall by Anatomical Therapeutical Chemical (ATC) Levels 2 and 4 for all subjects in the safety population. Prior and concomitant medications will be listed for all subjects in the safety population.

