11.1.3. Output Listings

Table 8: List of Output Listings

Title		Population	Programming Note	Deliverable
Disposition and Demographics				
16.2.1.1	Listing of Subject Disposition for Screen Failures	Screened		EOS
16.2.1.2	Listing of Subject Disposition	Randomized		EOS
16.2.1.3	Listing of Subjects who did not Satisfy Inclusion/Exclusion Criteria	Screened		EOS
16.2.1.4	Listing of Subject Randomization Details	Randomized		EOS
16.2.1.5	Listing of Major Protocol Deviations	Randomized		EOS
16.2.1.6	Listing of Subject Demographic and Baseline Characteristics	ITT-E		EOS
16.2.1.7	Listing of Medical History	ITT-E		EOS
16.2.1.8	Listing of Prior and Concomitant Medications	ITT-E		EOS
16.2.1.9	Listing of Additional OAB Medications	ITT-E		EOS
16.2.1.10	Listing of Additional OAB Procedures	ITT-E		EOS
16.2.1.11	COVID-19 Impact	ITT-E		EOS
16.2.1.12	Listing of Analysis Populations	Randomized		EOS
Efficacy				EOS
16.2.2.1	Listing of Bladder Diary	ITT-E		EOS
16.2.2.2	Listing of I-QOL Scores	ITT-E		EOS
16.2.2.3	Listing of OAB-q Scores	ITT-E		EOS
16.2.2.4	Listing of Patient Global Impression Scale Scores	ITT-E		EOS
16.2.2.5	Listing of Urodynamic Parameters	ITT-E		EOS
16.2.2.6	Listing of hSlo cDNA Concentrations	ITT-E		EOS
Safety				

Title		Population	Programming Note	Deliverable
16.2.3.1	Listing of Treatment Exposure	Safety		EOS
16.2.3.2	Listing of Adverse Events	Safety		EOS
16.2.3.3	Listing of Hematology Laboratory Results	Safety		EOS
16.2.3.4	Listing of Clinical Chemistry Laboratory Results	Safety		EOS
16.2.3.5	Listing of Urinalysis Laboratory Results	Safety		EOS
16.2.3.6	Listing of Vital Sign Results	Safety		EOS
16.2.3.7	Listing of ECG Results	Safety		EOS
16.2.3.8	Listing of Physical Examination	Safety		EOS
16.2.3.9	Listing of Post-void Residual Urine Volume	Safety		EOS
16.2.3.10	Listing of Clean Intermittent Catheterization	Safety		EOS
16.2.3.11	Listing of Bladder and Kidney Ultrasound	Safety		EOS

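### hSlo cDNA, the only summarised exposure result, is assigned to ITT-E and so grouped by randomised arm; after an identified dosing error it would be reported under a product the subject did not receive

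*SAP*

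**What the plan says.** Table 14.2.11, "Summary of hSlo cDNA Concentrations" (SAP 11.1.1), and Listing 16.2.2.6, "Listing of hSlo cDNA Concentrations" (SAP 11.1.3), both carry the population ITT-E and both stand under efficacy headings. The table is a topline as well as an end-of-study deliverable.

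SAP 3.1.4 defines membership and grouping for that population: "The ITT-E population consists of all subjects who are randomized and treated from Cohorts 1 and 2", and "Subjects will be included in the treatment group to which they are randomized". SAP 3.1.3 sets the contrasting rule for the safety population, which is made up of randomised subjects who "received study drug and will be used to analyze all safety endpoints based on actual treatment received". For listings, SAP 4.2.2 says: "The treatment group presented in listings will be based on the planned assignment for efficacy endpoints and actual assignment for safety endpoints".

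SAP 6.4, the analysis text for hSlo cDNA, asks for presence or absence by visit and for numeric summaries where cDNA is present. It names no population and no grouping rule. It sits in Section 6, where ITT-E is the general default.

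Protocol 3.2.3 classes hSlo cDNA as an other endpoint, neither efficacy nor safety, and Protocol 8.3 treats it as the pharmacokinetic assessment. SAP 7.1 plans no exposure summary, only a listing of the injection.

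SAP 3.2.1 includes among its major deviation categories "Subjects who received the wrong treatment", to be confirmed at unblinding.

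On a related label, SAP 5.4 states: "Prior and concomitant medications will be listed for all subjects in the safety population". It names the safety population for the summaries too. Tables 14.1.5.1 and 14.1.5.2 and Listing 16.2.1.8 nevertheless say ITT-E.

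**The concern.** Grouping by randomised arm suits an efficacy comparison, because it protects the comparison that randomisation created. hSlo cDNA answers a different question: whether the injected plasmid can be found in blood or urine, how much of it, and for how long. That result follows from the product in the syringe. A subject randomised to placebo who received URO-902 carries plasmid whatever her allocation.

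An exposure table grouped by allocation can therefore describe a product that some of its subjects never had. The adverse-event tables use the safety population and place the same subject by what she received, so the two topline outputs would put her in different columns. As Table 14.2.11 is the only summary of exposure in the plan, no other summary table would show the correct grouping.

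**Working it through.** No stated figure in the plan depends on this choice. Power, alpha and sample size are untouched. The check is a trace of labels followed by simple proportions.

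**Step 1: does the label change who is counted?** ITT-E is randomised and treated subjects from both cohorts (SAP 3.1.4). Safety is randomised subjects from both cohorts who received study drug (SAP 3.1.3). These are the same subjects. The only difference is the column in which each one appears.

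**Step 2: which grouping applies to hSlo cDNA?** Table 14.2.11 is ITT-E, ITT-E is by randomised arm, and SAP 6.4 contains no override, so the table is by randomised arm. For Listing 16.2.2.6 the same grouping is inferred from its ITT-E label and its efficacy heading, because SAP 4.2.2 gives a rule only for efficacy and safety endpoints.

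**Step 3: size of the effect, given an error.** Inputs are the planned arm sizes (SAP 1.2.1): 26 active and 13 placebo in each cohort. Placebo is pooled at the final analysis (SAP 1.2.3), giving 13 + 13 = 26.

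Case A assumes that one placebo-randomised subject receives URO-902 and tests positive, and that all true placebo subjects are negative.

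| Display | By randomised arm (current plan) | By treatment received |
|---|---|---|
| Pooled placebo, 26 | 1/26 = 3.8% | 0/25 = 0% |
| One cohort's placebo, 13 | 1/13 = 7.7% | 0/12 = 0% |

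SAP 6.4 summarises concentrations only where cDNA is present. In the placebo column that leaves one value, hers, so the placebo mean is the concentration of a subject who received URO-902.

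Case B assumes that one active-randomised subject receives placebo and tests negative, and that the other 25 in her arm are positive. The active arm's detection reads 25/26 = 96.2% by randomised arm and 25/25 = 100% by treatment received. Her absent value does not enter the concentration summary, so the arm's mean is the same under both groupings.

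**Step 4: how likely is Case A?** The documents give no misdosing rate. If each placebo-randomised subject had an independent probability e of receiving URO-902, the chance of at least one among 26 would be 1 − (1 − e)^26:

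- e = 0.5%: 12%
- e = 1%: 23%
- e = 5%: 74%

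These rates are assumptions, shown only to give a range. With e = 0 the two groupings give identical output.

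**Step 5: the medication labels.** SAP 5.4 says safety population; Tables 14.1.5.1 and 14.1.5.2 and Listing 16.2.1.8 say ITT-E. Concomitant medication is a safety endpoint in Protocol 3.2.2 and SAP 1.1.2, so the text of 5.4 agrees with SAP 3.1.3 and the appendix does not. This mismatch is visible on the page and needs no dosing error. Because membership is the same in both populations, it also changes no number without one. SAP 5.4 speaks of an overall summary, so any effect on the arm columns of those tables is uncertain.

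**The case against.** The strongest reply is that nothing changes unless a dosing error happens and is found. Grouping by actual treatment can move only a subject whose error is known; an undetected error sits in the wrong column under either label. A known error is already reported elsewhere: in the major deviation table (14.1.2.1) and listing (16.2.1.5), in the injection listing (16.2.3.1, Safety), and in the subject-level hSlo listing. With about 78 subjects, one misdosed subject can be traced by subject number. The endpoint is descriptive, with no interval or test planned. All of this stands and keeps the point small. It does not make the summary table correct, since the listings reveal the error but leave the table's columns as they are.

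It is also fair to say that the SAP is consistent with itself on hSlo cDNA. Section 1.1.3 heads it as another efficacy objective, Section 6.4 lies within the efficacy section, and ITT-E is the default there. A reader might infer a contradiction, but there is none on this endpoint. The choice is open to question because of what the assay measures. The text and the appendix conflict only on prior and concomitant medication.

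Three stronger readings are tempting and are not supported.

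- That a misdosed subject would dilute the dose arm's concentration. Case B shows that one given placebo lowers detection only. If concentration rises with dose, a 24 mg subject given 48 mg would raise the 24 mg summary.
- That exposure and safety could not be read together. The listings allow the link to be made.
- That the placebo row is the trial's check on assay contamination. Neither document gives it that role, and Protocol 8.3 has every subject sampled before treatment, which provides a reference within each subject.

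**Conclusion.** The point holds as a minor one. Table 14.2.11 and Listing 16.2.2.6 report a pharmacokinetic result by allocation, when the result depends on the product injected. After an identified dosing error the subject's result would be attributed to a product she did not receive, and her column would differ from the one she occupies in the adverse-event tables.

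The size is one subject per error: pooled placebo detection of 1/26 (3.8%) instead of 0/25, or 1/13 (7.7%) instead of 0/12 within a cohort, with a placebo concentration summary resting on her alone. This assumes that she tests positive, that all true placebo subjects are negative, and that the planned arm sizes are met. If no error occurs, the outputs are the same.

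The title phrase about exposure is limited to summarised results on purpose, because the injection listing is also an exposure output. The planned grouping of the hSlo listing is an inference from its label and heading. The prior and concomitant medication labels are a plain inconsistency between SAP 5.4 and the appendix and should be reconciled in any case.

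**What to change.** 1. In SAP 11.1.1 and 11.1.3, change the population of Table 14.2.11 and Listing 16.2.2.6 from ITT-E to Safety.
2. Add a sentence to SAP 6.4 stating that hSlo cDNA is summarised and listed by treatment actually received. The sentence is needed as well as the label, because SAP 3.1.3 and 4.2.2 tie actual treatment to safety endpoints and hSlo cDNA is not classed as one. SAP 6.4 names no population at present, so this is an addition, not a replacement.
3. Change Tables 14.1.5.1 and 14.1.5.2 and Listing 16.2.1.8 from ITT-E to Safety, to agree with SAP 5.4.

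The cost is three table labels, two listing labels and one sentence. No new data are needed, the set of subjects does not change, and sample size and power are unaffected.
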